#### 3.4.1. Inclusion Criteria

In order to be included in this study, subjects must meet the following criteria:

Inclusion Criteria	Rationale	Screening	Baseline
a) Written informed consent/assent obtained from subjects/subjects' parent(s) or legally acceptable representative indicating that they understand the purpose of and procedures required for the study and are willing to participate in it	Administrative	x	
b) Male or female, aged 2 through 75 years, inclusive	Administrative	Х	

Version Final 2.0

Inclusion Criteria	Rationale	Screening	Baseline

 
c) Diagnosis of PID with impaired antibody production, i.e.:
 
Diagnosis of common variable immunodeficiency (CVID) as defined by the European Society for Immuno-deficiencies (ESID)a/Pan American Group for Immunodeficiency (PAGID)b diagnostic criteria Or
 
X-linked agammaglobulinemia (XLA) as defined by ESID/PAGID diagnostic criteria
 
	Disease requirement	x	

 
d) Established replacement therapy with any IVIg reference preparation during the previous 6 months, including documentation of IgG trough levels
 
	Pretreatment requirement	х	
e) Established replacement therapy with a single IVIg reference preparation for at least 3 months prior to treatment start with BT595 at a 3- or 4-week schedule with a constant IVIg dose that did not change by ±20% of the mean dose, regular dosage intervals, and at least 1 IgG trough level of ≥5 g/L during the previous 3 months	Pretreatment requirement	Х	х

a ESID diagnostic criteria (European Society for Immunodeficiencies, 2006).
 b PAGID diagnostic criteria (Conley et al, 1999).

#### 3.4.2. **Exclusion Criteria**

Subjects are excluded from this study if they meet any of the following criteria:

Exclusion Criteria	Rationale	Screening	Baseline
a) Pregnancy or unreliable contraceptive measures or lactation period (females only)	Lack of suitability for study due to safety reasons	х	х
b) Known intolerance to immunoglobulins or comparable substances (e.g., vaccination reaction)	Lack of suitability for study due to safety reasons	х	х
c) Known intolerance to proteins of human origin or known allergic reactions to components of the study product	Lack of suitability for study due to safety reasons	х	х

Version Final 2.0

Exclusion Criteria	Rationale	Screening	Baseline

 
d) Participation in another clinical study within 30 days before entering the study or during the study and/or previous participation in this study
 
	Lack of suitability for study	х	x

 
e) Employee or direct relative of an employee of the Contract Research Organization (CRO), the study site, or Biotest
 
	Administrative	х	Х

 
f) Acquired medical conditions known to cause secondary immune deficiency, such as chronic lymphatic leukemia, lymphoma, multiple myeloma, as well as protein losing enteropathies and hypoalbuminemia
 
	Lack of suitability for study	х	x

 
g) Other medical condition, laboratory finding, or physical examination finding that precludes participation
 
	Lack of suitability for study	Х	x

 
h) Recent febrile illness that precludes or delays participation
 
	Lack of suitability for study due to safety reasons	х	х

 
i) Active infection and receiving antibiotic therapy for the treatment of this infection at the time of screening. Note: if the subject is deemed to be a screen failure due to a nonserious active infection requiring antibiotic therapy, the subject may be rescreened after the initial screening
 
	Lack of suitability for study	х	Х

 
j) Therapy with systemic steroids or other immunosuppressant drugs at the time of enrollment (current daily use of corticosteroids, i.e., >10 mg prednisone equivalent/day for >30 days. Intermittent corticosteroid use during the study is allowable, if medically necessary)
 
	Interference with study outcomes	Х	

 
k) History of thrombotic events (including myocardial infarction, cerebral vascular accident [including stroke], pulmonary embolism, and deep vein thrombosis) within the 6 months before treatment start with BT595 or the presence of significant risk factors for thrombotic events
 
	Lack of suitability for study due to safety reasons	Х	x

 
Therapy with live-attenuated virus vaccines within 3 months before start of the study
 
	Interference of IVIg with live-attenuated virus vaccines	х	

Exclusion Criteria	Rationale	Screening	Baseline
m) Selective, absolute immunoglobulin A (IgA) deficiency or known antibodies to IgA	Lack of suitability for study due to safety reasons	х	х
n) Positive diagnosis of hepatitis B or hepatitis C	Lack of suitability for study	х	х
o) Positive HIV test	Lack of suitability for study	х	Х

 
p) History of drug or alcohol abuse within the 12 months before treatment start with BT595
 
	Subject compliance	х	Х

 
q) Inability or lacking motivation to participate in the study
 
	Subject compliance	Х	Х

# 3.5. DETERMINATION OF SAMPLE SIZE

A minimum sample size of 50 evaluable subjects was considered sufficient to ensure a power of at least 80% to reject the null hypothesis of an acute serious bacterial infection rate greater or equal to 1.0 by means of a 1-sided test and a Type 1 error of 0.01 assuming a true underlying rate of acute serious bacterial infections of 0.5 per year. About 70 subjects will be enrolled (treated) to account for drop-outs.

The sample size contains at least 50 evaluable male or female subjects (2 to <76 years), including at least 20 pediatric subjects (i.e., young children [2 to <6 years], children [6 to <12 years] or adolescents [12 to < 17 resp. <18 years]) and at least 20 adult subjects.

According to FDA advice from January 12, 2017 for Pediatric Study Plan, age groups are defined as stated in the FDA 2016 guideline differently for the US: The age group of adolescents for the US is restricted to 12 to <17 years and therefore only subjects 2 to <17 years can be enrolled into the group of pediatric subjects (i.e., young children [2 to <6 years], children [6 to <12 years] or adolescents [12 to <17 years].

The above sample size number (to obtain at least 50 subject–years) and inclusion of at least 20 pediatric subjects with the age distribution representative of the subject population follows the advice provided by the EMA (EMA/CHMP/BPWP/94033/2007 rev. 2, 2010) and FDA (FDA, 2008) and FDA (FDA, 2016).

Full pharmacokinetic (PK) characterization at steady state is to be carried out in at least 20 adult subjects and all consenting pediatric subjects (EMA: 6 to <18 years; FDA: 6 to <17 years). Optional sparse sampling will be taken for young children (2 to <6 years).

# 3.6. TREATMENT ASSIGNMENT & BLINDING

All subjects receive BT595 infusions on dosage intervals of 3– or of 4– weeks. The initial dose and dosage intervals are consistent with the subject's prestudy IVIg treatment and the

initial dose and dosage interval are only changed if medically indicated. The change is at the investigator's discretion. This is an open-label study; therefore; there is no blinding.

# 3.7. ADMINISTRATION OF STUDY MEDICATION

The planned dose of BT595 is 0.2 to 0.8 g/kg body weight (2 to 8 mL/kg) administered as intravenous infusions at 3- or 4-week intervals for a treatment period of approximately 12 months.

**Infusion rate:** BT595 is infused intravenously at an initial rate of 0.3 mL/kg/h for 30 minutes, and increased to 1.4 mL/kg/h for a further 30 minutes. If well tolerated, the rate of administration is then gradually increased to a maximum of 2.0 mL/kg/h for the remainder of the first infusion. From the second infusion, in subjects who have tolerated the infusion rate of 2.0 mL/kg/h well, the rate may be gradually increased to 4 mL/kg/h, and if still tolerated well, it may be further increased gradually to 6 mL/kg/h, and to a maximum of 8 mL/kg/h.

From the second infusion, subjects' infusion rates may be individually tailored (i.e., a certain infusion rate for a certain time period) at the discretion of the investigator, but must start again at an initial infusion rate of 0.3 mL/kg/h. This means that the 30 minute interval could be shortened to less than 30 minutes if deemed appropriate for the subject. Changes in infusion rates (increases and/or decreases) and the respective time of day are to be documented.

# 3.7.1. Dose Changes during the Study

The subject's total immunoglobulin G (IgG) trough levels are assessed prior to each infusion at the local laboratory to allow immediate dose adjustment if a subject's trough level was below 5 g/L. Serum trough levels of total IgG  $\geq$ 5 g/L must be met throughout the study. If a subject's IgG level changes to <5 g/L, the subject's dose had to be adjusted to meet the target trough levels. Dose changes are made at the investigator's discretion and are following the dosage regimen detailed in Section 6.2 of the clinical study protocol (CSP).

Body weight is assessed before each study infusion in order to calculate an accurate dose for each subject's dose infusion. The investigator calculates the percentage change in the subject's body weight since the last assessment. If a subject's body weight changed by <5% from the weight used for the current dose, the total dose remains the same as the current dose. If a subject's body weight changed by  $\geq$ 5% from the weight used for the dose per weight (g/kg), is adjusted accordingly to maintain a constant dose in g/kg/infusion during the study.

Any changes in dose and the reason for the change in dose are recorded in the electronic Case Report Form (eCRF).

# 3.8. STUDY PROCEDURES AND FLOWCHART

For an overview of the timing of the clinical and laboratory measurements see the Flowchart of the Study below.

#### 3-Week and 4-Week Schedule

Study Schedule	Visit 3-week	V1	V2 BL	V 3-19	V 20
	4-week			V 3-15	V 16
	Week 3-week 4-week	W -4 to W 0	W 0	W 3-51 W 4-52	Up to W 54 Up to W 56
	Day 3-week 4-week	D -28 through D 0	D 1	Approx D 22-358 D 29-365	Approx Up to D 379 Up to D 393
Assessments	Periods	Screening	Tre	atmentª	Closing (Follow-up) a
Informed consent/assent		•			
Demographic data (incl. gender, date of birth, ethnic or	igin, height)	•			
Medical and surgical history (incl. drug history, prev history)	vious medication, disease	•	•		
Eligibility criteria (inclusion/exclusion)		•	•		
Physical examination b		•	•	•	•
Vital signs (pulse, blood pressure, temperature, respira	tory rate)	•	• c	• c	•
Body weight		•	•	•	
Pregnancy test d		•	•	•	•
Safety laboratory (hematology, coagulation, clinical che	emistry, urinalysis)	•	●e	•	•
Intravascular hemolysis parameters (incl. Coombs test hemosiderin)	, haptoglobin, hemoglobin,	•			•
Viral safety (retention samples)		•			•
Virus serology (hepatitis B, hepatitis C, HIV)		•			
Infusion of BT595			•	•	
Immunoglobulin G trough levels (total IgG)		•	● e	•	•
Immunoglobulin G trough levels (subclasses 1-4)			●f	●f	
Specific antibody trough levels			●a	●g	
Subject diary (paper) dispensed			•	•	
Collection and review of subject diary (paper)				•	•
Health-related quality-of-life assessment			•	•	•
Concomitant medications		•	•		
Adverse events			•		
Pharmacokinetic parameters for total IgG, IgG subclas	sses, and antigen specific			● h	

Approx = approximately; BL = baseline; D = day; incl = including; V = visit; W = week.

a A time window of ±2 days will be allowed for the treatment period visits and the closing (follow-up) visit; however, this time window will not apply for the PK assessments. Pharmacokinetic assessments will follow time point specific time windows.

b The physical examination will be followed-up with a verbal exchange (face-to-face) between the subject and the investigator 1 hour after the end of each infusion, and a verbal exchange (by telephone) 24 and 72 hours after the end of each infusion.

c Vital signs (pulse, blood pressure, respiratory rate) will be assessed within 30 minutes before each infusion, 15 to 30 minutes after the start of each infusion, 15 to 30 minutes after the end of each infusion, and 15 to 30 minutes after the start of any change in the infusion rate. The vital sign, temperature, will be recorded within 30 minutes before each infusion only.

d A pregnancy human chorionic gonadotropin test in serum will be taken for all female subjects ≥12 years of age or with presence of menstruation at screening. Urine pregnancy dipstick tests will be performed at all other study visits.

e Additional samples for safety laboratory assessments and total IgG will be taken at the end of the first BT595 infusion.

f Samples will be taken from subjects (6 to <76 years) at baseline and before the 7th/5th infusion of the 3-week/4-week schedule, respectively (i.e., this sample is the same sample as the predose sample for PK analysis).

 Samples will be taken from subjects (12 to <76 years) at baseline and before the 7th/5th infusion of the 3-week/4-week schedule, respectively (i.e., this sample is the same sample as the predose sample for PK analysis).

h At the 7th infusion (Week 18 [3-week schedule]) or 5th infusion (Week 16 [4-week schedule]), serum samples for the PK analysis of total IgG, IgG subclasses 1-4, and antigen specific IgG levels (anti-pneumococcal capsular polysaccharide, anti-hemophilus influenzae type B, anti-measles, anti-tetanus, anti-cytomegalovirus, and anti-HBs/hepatitis B) will be drawn from subjects (6 to <76 years for total IgG and IgG subclasses 1-4; 12 to <76 years for antigen specific IgG levels) at the following time points: predose (i.e., 10 to 30 minutes before the infusion), 10 to 30 minutes postinfusion (end of infusion), 4 and 24 hours postinfusion; and 4, 7, 14, 21 days (for the 3-week and the 4-week treatment schedule), and 28 days postinfusion (4-week schedule only). For pediatric subjects (2 to <6 years),

sparse sampling for PK analysis of total IgG only may be performed at flexible time points within specified time windows after the end of the infusion (note: these samples are optional).

Solest AG Protocol 99

# 4. ENDPOINTS

#### 4.1. PRIMARY EFFICACY ENDPOINT

The primary efficacy endpoint is the rate of acute serious bacterial infections (i.e., the mean number of acute serious bacterial infections per subject-year).

Acute serious bacterial infections include:

- Bacteremia or sepsis
- Bacterial meningitis
- Osteomyelitis/septic arthritis
- Bacterial pneumonia
- Visceral abscess

Specific diagnostic criteria for these infection types as given in the FDA guidance (Food and Drug Administration (FDA) Guidance for Industry: Safety, efficacy, and pharmacokinetic studies to support marketing of immune globulin intravenous (human) as replacement therapy for primary humoral immunodeficiency. June 2008) are used.

# 4.2. SECONDARY EFFICACY ENDPOINTS

- IgG trough levels (total IgG) before each infusion
- Rate of any infections (number per year)
- Rate of nonserious infections (number per year), defined as all infections not fulfilling the FDA-guidance "Diagnostic criteria for serious infection types" (as defined under 4.1)
- Time to resolution of infections
- Antibiotic treatment (number of days antibiotic treatment received per month and per year)
- Rate of time lost from school/work due to infections (number of days per month and per year) and their treatment (number of days treatment per month and per year)
- Hospitalization (number of days per month and per year overall and number of days per month and per year due to infection)
- Fever episodes (number of days per year)

# 4.3. EXPLORATORY EFFICACY ENDPOINTS

- Changes in health-related quality-of-life parameters:
  - a) Pediatric subjects (2 to <18 years) complete the Pediatric Quality of Life (Peds QL™) Measurement Model (child self-report and/or parent proxy-report).
  - b) all adult subjects complete the EuroQol Five Dimension (EQ-5D-3L™) Health Questionnaire
  - c) pediatric subjects (4 to <18 years) complete the youth version of the EQ-5D™ (EQ-5D-Y™) Health Questionnaire (child self-report or proxy-report). (Note for the US only: The age group of adolescents for the US is restricted to 12 to

<17 years and therefore only subjects 2 to <17 years can be enrolled into the group of pediatric subjects.)

#### 4.4. PHARMACOKINETIC ENDPOINTS

- IgG trough levels (total IgG) before each administration.
- IgG trough levels (subclasses 1-4) at baseline and before the 7th/5th infusion of the 3-week/4-week schedule, respectively (with the exception of pediatric subjects aged 2 to <6 years).

- IgG trough levels of specific antibody levels (anti-pneumococcal capsular polysaccharide, anti-hemophilus influenzae type B, anti-measles, anti-tetanus, anti-cytomegalovirus, and anti-HBs/hepatitis B) at baseline and before the 7th/5th infusion of the 3-week/4-week schedule, respectively (with the exception of pediatric subjects aged 2 to <12 years).

- Pharmacokinetic parameters at steady-state for: a) total IgG (2 to <76 years), b) antigen-specific IgG (12 to <76 years), and c) IgG subclasses (6 to <76 years).

# 4.5. SAFETY ENDPOINTS

Tolerability and safety of BT595 will be evaluated by:

- Adverse events.
- Changes in safety laboratory parameters (including standard clinical chemistry, hematology, coagulation, urinalysis; outside reference range and clinically relevant).
- Number of positive intravascular hemolysis test results (direct Coombs test, and other tests for detection/evaluation of intravascular hemolysis).
- Changes in vital sign parameters (body temperature, blood pressure, pulse rate, respiratory rate).
- Changes in physical examination parameters.

# 5. ANALYSIS SETS

## 5.1. ALL SUBJECTS ENROLLED SET

The All Subjects Enrolled Set includes all subjects who have given informed consent/assent to this study. Listings will be based on this set.

#### 5.2. SAFETY SET

The Safety Set (SAF) comprises all subjects who have received at least 1 dose of study medication. Subjects will be analyzed according to the treatment received. The SAF will be used for all analyses of safety endpoints.

#### 5.3. FULL ANALYSIS SET

The Full Analysis Set (FAS) includes all subjects following the principle of intention-to-treat. The FAS comprises all subjects who received at least 1 dose of study medication (i.e., there is no difference between the FAS and the SAF in this study). Subjects will be analyzed according to the treatment planned. FAS will be used for all analyses of efficacy endpoints.

### 5.4. PER-PROTOCOL SET

The Per-protocol Set (PPS) includes all subjects who are compliant with the study protocol without any major protocol deviations. Classification of protocol deviations as major or minor will be agreed upon at the Data Review Meeting (DRM) prior to database lock. The decision to carry out any analysis based on the PPS will be evaluated at the DRM. Any analysis based on the PPS will be performed for the primary efficacy endpoint as an additional analysis. Subjects will be analyzed according to treatment received.

#### 5.5. PK TROUGH SET

The PK Trough Set includes all subjects following the principles of the SAF for whom at least 1 trough concentration of total IgG in the age group 2 to <76 years and/or subclass IgG in the age group 6 to <76 years (measured in local laboratory) is available. All PK analyses involving trough concentrations will be conducted using the PK Trough Set.

The total IgG PK concentrations measured at the end of 1st infusion by local labs will be also presented for the PK Trough Set, but not used for the calculation of summary statistics of the trough concentration of total IgG.

Additional trough samples for the 5th/7th infusion measured centrally via separate analytical method for the dense PK characterization and used for the Dense PK Subset data will not be included in the PK trough set.

Upon review, complete profiles or only certain time points may be excluded from the summary of trough concentrations from subjects who did not receive proper study medication dosing or had out-of-window sampling.

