Q3W – dosing schedule for dose administration once per 3 weeks

Q4W - dosing schedule for dose administration once per 4 weeks

<sup>1 Total IgGs will be measured as trough concentrations prior each infusion in local laboratory, and in central lab for samples collected for the dense PK sampling

<sup>2 Subclasses of IgGs will be measured as trough concentrations at baseline and prior to 7th/5th infusion for 3 or 4 –week schedule respectively in local laboratory, and in central lab for samples collected for the dense PK sampling.

<sup>3 Anti-pneumococcal capsular polysaccharide, anti-hemophilus influenzae type B, anti-measles, anti-tetanus, anti-cytomegalovirus, and anti-HBs/hepatitis B concentrations will be measured at central lab (Biotest). This analysis is planned only for subjects 12 years and older.

<sup>4 Pre-dose samples collected within 10-30 min before the start of infusion. Post-infusion (EOI) samples collected within 10-30 min window from the end of infusion, PK sampling windows for 4 and 24 hrs post-infusion -  $\pm 1$  h; for 7, 14, 21 and 28 days -  $\pm 1$  d

<sup>5 For pediatric subjects (2 to <6 years), sparse sampling for PK analysis of total IgG only may be performed at flexible time points within specified time windows after the end of the infusion (note: these samples are optional)

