#### 9.4. ANALYSIS OF SERUM CONCENTRATIONS

# 9.4.1. Summary of Trough Concentrations for Total IgG, and IgG Subclasses 1-4 (PK Trough Set).

Trough concentrations measured by local lab (Total IgG) and by central lab (IgG subclasses) will be summarized for each type of analyte (total IgG, subclasses of IgG) by dosing regimen (Q3W, Q4W), whole population, each age category, and visits, combining all dose levels including baseline values for prior IVIG formulations used by subjects before start of treatment with BT595 to study. Additional summaries will also be provided by dose level divided into 3 bins (0.2-<0.4, 0.4-<0.6, 0.6-0.8 g/kg dose bins) according to dosing regimen. Based on the number of subjects per age category the summaries by dose level may combine all or specific age categories, e.g., pediatric vs adult to have sufficient number of data for descriptive statistics.

Age categories are based on FDA (FDA, 2016) and EMA (EMA/CHMP/BPWP/94033/2007 rev. 2) guidance for IVIG. Additionally FDA and EMA guidance on pediatric studies and PK in pediatric studies were taken into consideration for planning of PK analyses [Food and Drug Administration (FDA) Guidance for Industry: General Clinical Pharmacology Considerations for Pediatric Studies for Drugs and Biological Products. December 2014. Available from: http://www.fdanews.com/ext/resources/files/12-14/12-08-14pediatricguidance.pdf?1418077303; European Medicines Agency Guideline ICH Topic E 11 Clinical Investigation of Medicinal Products in the Paediatric Population. January 2001. Available from:

http://www.ema.europa.eu/docs/en\_GB/document\_library/Scientific\_guideline/2009/09/W C500002926.pdf; European Medicines Agency Guideline On The Role Of Pharmacokinetics In The Development Of Medicinal Products In The Paediatric

Population. June 2006. Available from:

http://www.ema.europa.eu/docs/en\_GB/document\_library/Scientific\_guideline/2009/09/W C500003066.pdf].

Summary statistics will not be presented if 50% or more of the actual values for the PK sets at any 1 time point or bin are BLQ or missing or less than 3 values are available. The reporting will be limited to median value for n=1 and to median, min and max values for  $1 < n \le 2$ .

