#### 9.6.3. Figures for Baseline and Steady State Trough Levels

Steady state trough concentrations will be measured for all subjects for total IgG, and predefined age categories for the IgG subclasses (6 to <76 years) and antigen-specific IgG (12 to<76 years). Total IgG and IgG subclasses trough concentrations for baseline and predose for 7th/5th infusion (Q3W / Q4W) will be available from (Total IgG) and central (IgG subclasses) lab for all subjects in all age categories. Trough concentrations obtained as a

part of Dense PK sampling will not be included in the figures. All antigen-specific IgG trough concentrations for the Specific IgG Trough PK Set will be only available from central lab (Biotest).

Data will be presented by Box-whisker plots for the 2 time points. A first set of figures will present baseline (which is the trough concentration of a similar product used by subjects previously to the study) and steady state data for all subjects together, and Q3W and Q4W separately on the same graph (6 boxes). Separate figures will be provided for each of the IgG variable (total IgG, 4 subclasses, and 6 antigen-specific IgGs).

A similar set of figures will present baseline and steady state levels for each age categories (FDA, EMEA categories on separate graphs) for each dosing interval and for each IgG variables on separate figures (total IgG, 4 subclasses, and 6 antigen-specific IgG).

Additionally, figures for different age categories will be produced for dose-normalized steady-state concentration  $C_{ss}/D$  for total IgG, IgG subclasses, and specific IgGs after the 7th BT595 infusion for Q3W schedule or the 5th infusion for Q4W schedule by age category on the same box plot.

Finally, a figure representing only the steady state concentrations of total IgG measured once in local lab and once in central lab for the subjects participating to the PK dense sampling will be presented by Box-whisker plots for the 2 measurement methods, see Section 9.4.3 (Multiple PK set).

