#### 9.7. EXPLORATORY COMPARISON OF STEADY-STATE TROUGH CONCENTRATIONS FOR TOTAL IGG, IGG SUBCLASSES, AND SPECIFIC IGGS WITH PREVIOUS IGG FORMULATION

Exploratory comparison of  $C_{ss}$  and dose-normalized  $C_{ss}/D$  between BT595 and similar products (IVIG products) will be performed for age categories and overall by ANOVA. The data for PK Trough Set and Specific IgG Trough PK Set will be used.

Log-transformed parameters Css/D for total IgG, IgG subclasses and specific IgGswill be compared separately by dosing interval and by age category where possible with treatment as fixed effect and subject as random effect based on existing guidance on bioequivalence from EMA (European Medicines Agency Questions and Answers: positions on specific questions addressed to Pharmacokinetics and FDA (Food and Drug Administration (FDA) Guidance for Industry). The following hypotheses will be tested for Css values:

Ho1:  $\mu_T/\mu_R \le 80\%$  vs. Ha1:  $\mu_T/\mu_R > 80\%$  and Ho2:  $\mu_T/\mu_R \ge 125\%$  vs. Ha2:  $\mu_T/\mu_R < 125\%$ 

The same model will also be repeated for dose normalized trough concentration.

If the 90% CI for the geometric mean ratio (GMR) is within (80% - 125%) for any of the contrasts for the parameters Css/D, the null hypotheses, that is H01 and H02, will be rejected with conclusion that the administration with BT595 (T=Test) is equivalent to administration of the previous IgG formulation (R=Reference).

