# 13. CHANGE FROM ANALYSIS PLANNED IN PROTOCOL

## 13.1.1. Specific IgG Trough PK Set

Specific IgG Trough PK Set was added to the definition of PK Sets to distinguish between trough concentration for Specific IgG measured at central lab unlike trough concentrations for total IgG and IgG subtypes measured at local labs.

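### The SAP does not settle which laboratory's IgG subclass troughs enter the exploratory comparison of BT595 with previous IVIg

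*SAP*

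**What the plan says.** **Local laboratory for subclass troughs**
- SAP 5.5 admits a subject to the PK Trough Set if a trough of total IgG and/or "subclass IgG in the age group 6 to <76 years (measured in local laboratory) is available".
- SAP 9.3, Table 1 footnote 2: "Subclasses of IgGs will be measured as trough concentrations at baseline and prior to 7th/5th infusion". The sentence goes on to assign these troughs to the local laboratory, and the dense-PK samples to the central one.
- SAP 13.1.1 explains that specific IgG was given its own set because it is measured centrally, "unlike trough concentrations for total IgG and IgG subtypes measured at local labs".

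**Central laboratory for subclass troughs**
- SAP 9.4.1, headed as a PK Trough Set summary: "Trough concentrations measured by local lab (Total IgG) and by central lab (IgG subclasses) will be summarized". The lead-ins to its tables repeat this.
- SAP 9.6.3 gives the central laboratory for subclass troughs at both baseline and predose 7th/5th infusion.

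**Which sample, and which set**
- SAP 3.8, flowchart footnote f, on the subclass sample before the 7th/5th infusion: "this sample is the same sample as the predose sample for PK analysis". Protocol 7.1 agrees, and protocol 9.5.2 sends PK samples, predose included, to the central laboratory.
- SAP 5.5 keeps "Additional trough samples for the 5th/7th infusion measured centrally via separate analytical method" out of the PK Trough Set where they serve the Dense PK Subset.
- SAP 9.6.3 adds that troughs obtained as "part of Dense PK sampling will not be included in the figures".
- SAP 9.7, for the comparison with previous IVIg: "The data for PK Trough Set and Specific IgG Trough PK Set will be used". Its contrasts cover total IgG and subclasses 1-4, 7th/5th infusion against baseline.

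**The concern.** The study is uncontrolled, so the trough on the patient's previous IVIg is its only within-patient reference. SAP 9.7 allows a conclusion of equivalence if the 90% confidence interval for the test/reference geometric mean ratio lies within 80% to 125%. Such a ratio describes the products only if both values come from one assay. The SAP itself treats the laboratory as material: it calls the central measurement a different method and separates the specific IgG set on that ground.

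For subclasses the written rules cannot all be followed, so a programmer has to choose. Some choices give a valid pair. Others give a pair in which laboratory and product are confounded, or no BT595 value at all. The planned local-against-central figure in 9.6.3 covers total IgG only, so it would not reveal a laboratory effect in the subclasses.

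**Working it through.** The plan states no figure on this point, so the check is a cross-reading, followed by an illustration of what a mixed pair would do.

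**Step 1. The possible readings of the subclass contrast in 9.7**

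| Passages followed | Baseline | Before 7th/5th infusion | Result | What it contradicts or lacks |
|---|---|---|---|---|
| SAP 5.5, Table 1 footnote 2, 13.1.1 | local | local | same laboratory | 9.4.1, its tables, 9.6.3; also needs a local subclass result from the shared predose sample, which the protocol does not describe |
| SAP 9.4.1, 9.6.3 | central | central | same laboratory | the local wording and the exclusion in 5.5; footnote 2; 13.1.1; and, through footnote f, the exclusion in 9.6.3 itself |
| Footnote f, protocol 9.5.2, exclusion in SAP 5.5 applied | either | central only, excluded | no BT595 value | leaves 9.7 without its test value |
| As above, central value admitted, baseline kept local | local | central | mixed | the exclusion in 5.5; prescribed by no passage |

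Each of the first two readings gives a like-for-like pair, and each breaks at least one written rule.

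**Step 2. Where the conflict stops**
- Total IgG troughs are local in SAP 5.5, Table 1 footnote 1 and 9.4.1. The exclusion in 5.5 removes only their second, central measurement.
- Specific IgG is central in SAP 5.6, Table 1 footnote 3 and 9.4.2.
- The primary endpoint uses no IgG assay.

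**Step 3. Effect of a mixed pair**

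Let L be the central/local assay ratio. With a local baseline and a central steady-state value:

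reported ratio = true ratio × L.

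Dividing by dose does not remove L. The documents give no value for L. If the assay difference is assumed to be 10%, 15% or 25%, a true ratio of 1.00 is reported as 0.90-1.10, 0.85-1.15 or 0.75-1.25. The error can also hide a difference: a true ratio of 0.80 with L = 1.25 is reported as 0.80 × 1.25 = 1.00.

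**Step 4. Illustration against the 80-125% rule**

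All inputs here are assumptions: true ratio 1; n = 10 or 20 pairs; within-subject CV of 10%, 15% or 20%; log differences normal with mean ln L and SD √2 × √ln(1 + CV²); 40,000 simulated studies per cell. Entries are the percentage of studies whose 90% t-interval lies within 80-125%.

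| CV | n | L = 0.80 | 0.85 | 0.90 | 1.00 | 1.10 | 1.15 | 1.25 |
|---|---|---|---|---|---|---|---|---|
| 10% | 10 | 4.7 | 35.1 | 78.7 | 99.7 | 83.8 | 53.4 | 5.1 |
| 10% | 20 | 5.2 | 58.1 | 97.4 | 100.0 | 98.9 | 81.5 | 4.8 |
| 15% | 10 | 5.1 | 21.1 | 49.7 | 85.0 | 54.3 | 31.2 | 5.0 |
| 15% | 20 | 5.0 | 34.3 | 77.4 | 99.6 | 83.2 | 52.8 | 4.9 |
| 20% | 10 | 5.0 | 14.9 | 30.3 | 51.2 | 33.8 | 20.7 | 4.7 |
| 20% | 20 | 5.0 | 23.8 | 56.5 | 92.8 | 62.5 | 35.9 | 5.2 |

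With no laboratory difference the chance of meeting the rule is 51-100%. At L = 0.85 it is 15-58%, at L = 1.15 it is 21-82%, and at L = 0.80 or 1.25 about 5%. A mixed pair would therefore matter if one were formed.

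**The case against.** The strongest reply is that the SAP foresees two laboratories and keeps them apart. Section 9.4.3 has steady-state troughs measured in both and summarised separately: local for the PK Trough Set, central for the Dense PK Subset. Section 6.5 allows the two sources to be separated. Read this way, the exclusion in 5.5 removes a second measurement and guards against mixing. One shared sample need not mean one assay, since protocol 9.5.2 speaks of an aliquot being stored and measured centrally. Table 1 footnote 2, read to its end, gives local values at both time points.

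Much of this stands. A reader might infer that the subclass contrast must be either empty or a local baseline against a central steady-state value. The documents do not support that: footnote 2 gives local values at both time points, 9.6.3 gives central values at both, and no passage pairs a local baseline with a central steady-state value. A reader might also infer that a subclass change from the previous-IVIg baseline is at risk. No such analysis is specifically planned: 8.2.1 concerns total IgG, and the change-from-baseline analysis in 9.5.1 takes the dense-PK predose value as its baseline.

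The analysis is also modest in rank. Section 9.7 is headed exploratory, and protocol 10.10 describes the intra-individual comparison under total IgG troughs, without formal testing.

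The reply does not remove the contradiction. The local-local reading still conflicts with 9.4.1, its tables and 9.6.3, and the central-central reading still conflicts with 5.5, footnote 2 and 13.1.1.

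**Conclusion.** The point holds as an unresolved contradiction in the SAP. The laboratory and analysis-set rules for subclass troughs cannot all be followed, and the choice decides whether the comparison with previous IVIg is like for like, mixed or without a BT595 value. Within that comparison the exposure is limited to the exploratory subclass contrasts in 9.7 and the subclass box plots in 9.6.3.

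The size of any bias is unknown. It arises only if mixed pairs are formed, and it would then equal the central/local assay ratio, which the documents do not give. The percentages above illustrate sensitivity under assumed inputs and do not predict what this trial would show.

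The documents also do not show where the baseline subclass serum was assayed, so they do not establish that the central laboratory is the right choice.

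**What to change.** - Name one laboratory and method for subclass troughs at both baseline and before the 7th/5th infusion, choosing whichever laboratory actually holds both values.
- Align SAP 5.5, Table 1 footnote 2, 9.4.1 with its tables, 9.6.3, 9.7 and 13.1.1 with that choice.
- If the laboratory is central, limit the exclusion of central 5th/7th-infusion troughs in 5.5, and of dense-PK troughs in 9.6.3, to total IgG.
- In 9.7, model only pairs from the same laboratory, list subjects without such a pair, and report the subclass contrast as not estimable if there are none.

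The cost is SAP wording and one programming filter. The downside is that subjects without a same-laboratory pair drop out of the subclass contrast. Their number cannot be derived from the documents; if baseline and steady-state values sit in different laboratories throughout, it would be all of them.
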